# **REVISION HISTORY**

Revision #	Version Date	Summary of Changes	Consent Change?
Version 2	05/03/22	Add 97 subjects to the protocol that were already recruited for interview, focus groups and usability testing. This along with the 50 subjects that can be enrolled in the trial at HCMC, brings the total maximum enrollment to 147.	No

## ABBREVIATIONS/DEFINITIONS ABBREVIATIONS/DEFINITIONS

EMR Electronic Medical RecordHHS Hennepin Healthcare System

HHRI Hennepin Healthcare Research Institute

• HIPAA Health Insurance Portability and Accountability Act of 1996

IRB Institutional review boardITS2 Internal Transcribed Spacer 2

• PI Principal Investigator

PHI Protected Health Information

SRTR Scientific Registry of Transplant Recipients

UMN University of Minnesota
 FDA Food and Drug Administration
 RCT Randomized Controlled Trials

OPTN Organ Procurement and Transplantation Network
AHRQ Agency for Healthcare Research and Quality

• USRDS United State Renal Data System

• BMT Bone Marrow Transplant

• ICS Informatics Consulting Services

ISRS International Standard on Related Services
 CTSI Clinical and Translation Science Institute

• FWA Federal wide Assurance

HSCT Hematopoietic Stem Cell Transplant

ITT Intention-to-treatIE Information Exchange

•

## 1.0 Objectives

## 1.1 Purpose:

[figure not shown]
Evaluate the effectiveness of the patient-centered SRTR report card among kidney transplant candidates. A randomized controlled trial (RCT) of all transplant candidates evaluated at the Hennepin Healthcare System (HHS) transplant centers will be conducted. One group with be shown the existing SRTR report cards and then the new patient-centered report cards (funded by AHRQ) on the web. The new patient-centered report cards were developed with feedback from the general public, local transplant candidates, their family members and national transplant recipients. The feedback was collected using data from emails and phone calls received by SRTR, Amazon Mechanical Turk randomized surveys, interviews and focus groups and subsequent usability testing of functioning prototypes with local candidates. (n=97 for subjects in interviews and focus groups and usability testing).

## 2.0 Background

## 2.1 Significance of Research Question/Purpose:

On average, every 10 minutes someone is added to the organ transplant waiting list (1). Previous studies have shown that kidney transplant is a more effective treatment than dialysis (2). For patients with end-stage liver, heart, or lung disease, life is often not sustainable without a transplant. However, on average, every day 79 patients undergo transplant but 18 others die waiting (1). Mortality on the waiting list remains high. Thus, transplant is cost effective (3-8). Chronic comorbid conditions are increasingly common (9). Most transplant candidates have end-stage organ failure due to a variety of chronic diseases, and thus represent a priority AHRQ population.

Figure 1: Adjusted adult graft survival hazard ratios for kidney, heart, liver, and lung transplant centers, from publicly available SRTR report cards.

- 2.2 Preliminary Data: Our preliminary data and other data suggest room for improvement in quality and efficiency of care. Using SRTR's publically available PSRs, we described the variation in risk-adjusted hazard ratios for allograft failure at 1-year post transplant for all solid organ transplant centers (Figure 1). Allograft failure was defined as return to dialysis, transplant, or death. We also surveyed all kidney transplant centers in the US and showed considerable variation in the structure and process of care (10). The PI and collaborators have shown that the structure and process of care plays a role in patient adherence to immunosuppressive medications (11). Others have shown variation in aggressiveness of liver transplant centers (12, 13).
- 2.3 Relevance to proposed work: Variation in post-transplant outcomes and in risk tolerance at transplant centers is not known to all patients. Informing patients of their choices through our innovative study can improve their chances of undergoing transplant and improve post-transplant outcomes.

Dissemination of a new website and a printout of SRTR report cards that will be functional even after the proposed project is completed: The proposed project will deliver a new website and printouts of the SRTR report cards, which SRTR will use to provide information to the public about each transplant center in the country. Since this project is being carried out by [name], SRTR Medical Director (PI on this proposal), the final website will likely be adopted for use by SRTR. SRTR and OPTN lack the qualitative and design collaborators and easy access to transplant candidates needed to carry out the project. Therefore, the project team will develop and evaluate patient-centered SRTR report cards that will effectively communicate comparative information to transplant candidates on their alternatives when choosing transplant centers.

In the future, SRTR staff can also inform patients and their family members about the new patient-friendly website. The SRTR website will prominently display a link for patients and their family members. This website currently receives more than 100,000 hits annually and the most common hits are to the section that displays the report cards.

**Potential for the proposed project to improve outcomes:** We will *change the paradigm* for how patients choose a transplant center by using report cards tailored to an individual's clinical profile, thereby improving a broad set of patient-centered outcomes, effectively navigating the system of transplant centers with varying candidate acceptance criteria, creating greater satisfaction with the center selection process, and resulting in potentially better post-transplant outcomes. Transplant candidates could use the website to refer themselves directly to centers with better outcomes, thereby becoming *empowered*. Candidates who are turned down at one center could use the report card to find other centers more likely to transplant patients like them. Such public information is also likely to change transplant center behavior (14-16). Centers currently unwilling to transplant high-risk candidates could see patients choosing a nearby center that does transplant such candidates. This

could motivate a risk-averse center to review its practices and potentially accept more high-risk candidates. Thus, the patient-centered report cards can provide incentives to improve access to transplantation.

## 3.0 Study Endpoints/Events/Outcomes

- 3.1 Primary Endpoint/Event/Outcome: The primary outcomes are two separate assessments of the comprehension of the report card. To assess comprehension, the correct response to the following type of question will be assessed, "Which of the following transplant centers have the most experience with transplanting candidates over age 70?" There will be one correct answer; respondents will be told to assume they are in a specific zip code or state and are over age 70 and then asked to choose one of the several transplant center report cards shown or respond "Don't know." Another example of the question used to assess comprehension will be used, "Which of the following transplant centers have the most experience with transplanting candidates with body mass index (BMI) over 40?" There will be one correct answer; respondents will be told to assume they are in a specific zip code or state and have a BMI over 40 and then asked to choose one of the several transplant center report cards shown or respond "Don't know." Similar measures used previously by [name], to determine the best way to present report cards to the general public (17). We will also determine comprehension of key concepts in the reports, to identify participants' ability to determine whether a center performs transplants on "patients like me."
- 3.2 Secondary Endpoint(s)/Event(s)/Outcome(s): Perceived value of information will be determined via patient responses to the following question, "How useful is the information in the report card in helping you choose a transplant center for you or your family?" Response choices to the questions will be based on a 5-point Likert-type scale (Example: 1 = not at all useful to 5 = very useful). We will also measure satisfaction with decision-making and decisional conflict using the effective decision subscale of the Ottawa Decisional Conflict Scale, which has been validated in multiple studies (18-21).

These questions will be written on cards if the intervention is conducted face-to-face. If conducted via HIPPA compliant zoom call, the questions will be placed in the chat box for the subject to refer to them during the intervention.

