## 4.0 Study Intervention(s)/Interaction(s)

#### 4.1 Description:

Before the intervention, the study design with use of hypothetical scenarios will be explained to the participant. The concept of randomization will be also be explained. The participants will be asked a few questions to assess their understanding of the study design, specifically the hypothetical nature of the scenarios. We will also assess whether they understand the concept of being randomized to see one

website first and then the other. Only those participants that understand the study design will be invited to participate in the intervention and will be randomized. For subjects that are randomized, a survey will be administered verbally to collect demographic information and information about their kidney disease and comorbidities. The functional health literacy and numeracy assessment and health status questionnaire will be completed. Subjects will be stratified by the transplant center site and then block randomized. One group will be shown the existing SRTR website with its existing SRTR report cards and then the website with the new patient-centered AHRQ report cards for kidney transplants. The other group will be shown the two websites in opposite order. Each participant will have at most 30 minutes to view each of the websites. After viewing each website, responses to the intervention will be collected. Sessions where participants are reviewing the websites will be recorded using Zoom. Figure 2 shows the study design whereby subjects will be block randomized once to one of the four groups consisting of 18 subjects each. At the end of the study, the patients will have access to both the websites.

The study interventions can be administered in person on a laptop. During the COVID-19 pandemic, the intervention can be administered remotely via email and zoom. The link to the websites will be sent via encrypted email and the intervention will be recorded via zoom. The recordings for subjects at Hennepin Healthcare will be stored on computers at that site.

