If participant does not have your own electronic device or internet, the study will send the participant a study iPad with internet that participant can use for the intervention and then to send back to the study team. We will provide detailed instructions on how to use the iPad and Zoom application. The study will also pay for a FedEx pick up from the participants' home to return the iPad to the study team after the completion of the intervention.

Figure 2: Study Design of the Randomized Trial.

**Study Design** 36 subjects per organ type randomized to see 36 Subjects per organ type randomized to see SRTR website first AHRQ website first. 18 subjects (30 min) 18 subjects (30 min) 18 subjects (30 min) 18 subjects (30 min) Primary Outcome: Which **Primary Outcome: Primary Outcome:** Primary Outcome: Which Which of the following Which of the following of the following transplant of the following transplant transplant centers have transplant centers have centers have the most centers have the most the most experience with experience with the most experience with experience with transplanting candidates transplanting candidates transplanting candidates transplanting candidates over age 70? with BMI over 40? over age 70? with BM! over 40? Then subject will see Then subject will see SRTR Then subject will see Then subject will see AHRQ website. (30 min) SRTR website. (30 min) website. (30 min) AHRQ website. (30 min) Primary Outcome: Which Primary Outcome: Which Primary Outcome: Which **Primary Outcome:** of the following transplant of the following transplant Which of the following of the following transplant centers have the most centers have the most transplant centers have centers have the most experience with experience with the most experience with experience with transplanting candidates transplanting candidates transplanting candidates transplanting candidates over age 70? over age 70? with BMI over 40? with BMI over 40?

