# 11.0 Number of Participants

## 11.1 Number of Participants to be Consented

The table shows the required sample size for ranges of detectable differences and within-person correlation.

						Correlation			
							0.		
		0.0	0.1	0.2	0.3	0.4	5	0.6	
Ī	0.20	107	98	89	79	67	56	45	

Detectable	0.22	90	82	76	66	56	47	38	
Difference	0.24	76	71	64	55	48	40	33	
	0.25	70	66	59	51	44	37	*	
	0.26	66	61	55	48	41	34	*	
	0.28	57	53	46	41	35	30	*	
	0.30	51	45	41	36	32	27	*	

On the conservative side, we will power the study to detect a proportional difference as small as 25% and therefore plan to enroll at 72 subjects for each organ trial. Recruitment will continue until this desired sample size is achieved. Given the low-risk nature of this project, there will be no stoppage rules based on interim analysis for recruitment.

This 72 is in addition to the 130 subjects enrolled in the interviews and focus groups and usability testing. Thus the total enrollment will be 130 + 72 = 202. The 97 subjects already enrolled along with the 50 subjects that can be enrolled in the trial at HCMC, brings the total maximum enrollment to 147 at HCMC.

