#### 17.0 Statistical Considerations

#### 17.1 Data Analysis Plan:

Before initiating outcome analyses, we will perform exploratory analysis to examine frequency distributions for all baseline variables, with particular attention to variable ranges and skewness. We will examine group comparability at baseline between the two RCT arms to assess whether randomization succeeded in creating equivalent groups. These analyses will help determine potential need to incorporate additional covariates in later analyses using propensity-based methods (22-25). Relevant baseline measures include socio-demographic factors, health literacy and numeracy assessment, and baseline survey information.

17.2 Power Analysis: The table shows the required sample size for ranges of detectable differences and within-person correlation.

						Correlation		
							0.	
		0.0	0.1	0.2	0.3	0.4	5	0.6
	0.20	107	98	89	79	67	56	45
Detectable	0.22	90	82	76	66	56	47	38
Difference	0.24	76	71	64	55	48	40	33
	0.25	70	66	59	51	44	37	*
	0.26	66	61	55	48	41	34	*
	0.28	57	53	46	41	35	30	*
	0.30	51	45	41	36	32	27	*

On the conservative side, we will power the study to detect a proportional difference as small as 25% and therefore plan to enroll at 72 subjects. Recruitment will continue until this desired sample size is achieved.

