## 17.3 Statistical Analysis:

The primary analysis will be based on the conservative "intention-to-treat" (ITT) approach. We will use a chi-square test and logistic regressions for analyzing primary and secondary measures. A sensitivity analysis will be conducted excluding subjects that did not enter the correct hypothetical information into the website. The research coordinator will record the amount of time subjects spend with each website and the webpages viewed by each subjects and that information will be analyzed for descriptive analysis. Other subset analysis will be conducted but presented as ad hoc analysis.

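### The plan does not say whether the age and BMI comprehension questions are pooled or tested as two primaries, or that the primary test is paired; 72 subjects suffice for a pooled comparison, not for each question at about 36 per website.

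*Combined protocol and SAP*

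**What the plan says.** Section 3.1 opens with "The primary outcomes are two separate assessments of the comprehension of the report card". It presents the age-over-70 question as a type of question, introduces the BMI-over-40 question with "Another example of the question used to assess comprehension will be used", and adds "We will also determine comprehension of key concepts in the reports" without saying whether that measure is primary or secondary.

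Section 4.1 says "subjects will be block randomized once to one of the four groups consisting of 18 subjects each". Figure 2 shows two website orders of 36, each split into 18 and 18. The extracted text lists two age boxes and two BMI boxes at each viewing. Responses are collected after each website, so every subject contributes two answers.

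Sections 11.1 and 17.2 carry the same table, introduced by "The table shows the required sample size for ranges of detectable differences and within-person correlation". Its 0.25 row reads 70, 66, 59, 51, 44, 37 at correlations 0.0 to 0.5, with an asterisk at 0.6. Section 17.2 concludes: "we will power the study to detect a proportional difference as small as 25% and therefore plan to enroll at 72 subjects". Neither section gives alpha, power, base rates or the test.

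Section 17.3 says: "We will use a chi-square test and logistic regressions for analyzing primary and secondary measures". It does not mention pooling of the questions, pairing, or a success rule. Its sentence labelling other subset analyses as ad hoc does not name the two questions.

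**The concern.** Two analyses are compatible with the text. One pools correct answers over both questions and compares the websites once. The other tests the age and BMI questions as two primary outcomes, each on half the subjects. They differ in the hypothesis tested and in power. If the plan does not choose, the choice can be made after the answers are known.

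There is also a gap between sample size and analysis. The table relies on within-person correlation, whereas section 17.3 names a chi-square test and says nothing about the two answers coming from the same person. An ordinary Pearson chi-square treats them as independent and does not hold its nominal 5% level.

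**Working it through.** **Inputs from the plan.** 72 subjects; 4 × 18 groups; difference 0.25; the 0.25 row of the table in 11.1 and 17.2.

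**Assumptions, not in the plan.** Two-sided alpha 0.05, 80% power, exact McNemar test, proportions symmetric about 0.5 (0.375 v 0.625 for a difference of 0.25).

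**Step 1: reproduce the table.** With p1 = 0.5 − d/2, p2 = 0.5 + d/2 and correlation r, let c = r × √[p1(1−p1)p2(1−p2)]. The discordant probabilities are p1(1−p2) − c and p2(1−p1) − c. For d = 0.25, √[…] = 0.375 × 0.625 = 0.234375, so:
- r = 0: 0.1406 and 0.3906
- r = 0.3: 0.0703 and 0.3203
- r = 0.5: 0.0234 and 0.2734
- r = 0.6: 0 and 0.25

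The last line is the limit: the largest possible correlation is 0.375/0.625 = 0.60. The plan gives an asterisk there.

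Smallest number of pairs with at least 80% power:

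| r | 0 | 0.1 | 0.2 | 0.3 | 0.4 | 0.5 |
|---|---|---|---|---|---|---|
| Plan | 70 | 66 | 59 | 51 | 44 | 37 |
| Recomputed | 71 | 65 | 58 | 51 | 44 | 37 |

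Every filled cell of the whole table agrees within 1 subject. The table is therefore consistent with one paired comparison, counted in subjects.

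**Step 2: subjects per question.** Two of the four groups of 18 see a given question at each viewing: 2 × 18 = 36. Balanced over the two orders, that is about 36 answers per question per website. These are 36 pairs if a subject's question repeats on the second website, or 36 v 36 different subjects if it switches.

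**Step 3: compare with the 0.25 row.** Pooled: 72 is at or above every filled cell (largest 70). Per question: 36 is below every filled cell, by 70 − 36 = 34 at r = 0 and by 37 − 36 = 1 at r = 0.5.

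**Step 4: power for 25 points (0.375 v 0.625).**

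| | r = 0 | 0.3 | 0.5 |
|---|---|---|---|
| Pooled, 72 pairs, exact McNemar | 81% | 93% | 99% |
| Pooled, 72, unpaired chi-square | 87% | 91% | 95% |
| Per question, 36 pairs, exact McNemar | 47% | 62% | 79% |
| Per question, 36 pairs, uncorrected McNemar | 57% | 70% | 87% |
| Per question, 36, unpaired chi-square | 56% | 56% | 57% |

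At r = 0.6, for which the plan gives no figure, 36 pairs give 92% (exact McNemar) and the unpaired chi-square gives 58%.

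**Step 5: sensitivity to base rates.** For 36 v 36 different subjects by chi-square, power for 25 points at lower rates 0.10 / 0.20 / 0.30 / 0.375 / 0.50 / 0.60 / 0.70 is 74 / 64 / 57 / 56 / 61 / 68 / 85%. For 36 pairs by exact McNemar, a lower rate of 0.10 gives 63% at r = 0 and 80% at r = 0.3; a lower rate of 0.70 gives 74% at r = 0 and 83% at r = 0.2.

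**Step 6: level of an unpaired chi-square on paired answers.** In large samples the true two-sided error is 2 × P(Z > 1.96/√(1−r)), which is 0.019 at r = 0.3 and 0.006 at r = 0.5. Simulation with 72 subjects and a common rate of 0.5 gives about 0.02 and 0.007, against the nominal 0.05.

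**The case against.** The strongest reply is that pooling was intended. Section 3.1 treats the two questions as examples of one type, and a single within-person table fits one comparison better than two. The phrase about two separate assessments could refer to the two viewings, since Figure 2 repeats the primary outcome after each website. A chi-square test could also mean McNemar's, whose statistic is referred to a chi-square distribution, and section 17.3 also names logistic regression. All of this stands as a plausible reading. It does not settle the matter, because no section says that the questions are pooled, names a paired test, or describes how a regression would handle two answers per person.

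Four stronger readings are tempting but not supported.
- **That the sample-size table is wrong or the trial is underpowered.** The table reproduces, and 72 is adequate for a pooled comparison. The shortfall exists only if each question is tested alone.
- **That 56 to 58% is the plan's power, or that an unpaired chi-square can never reach 80% with 36 per website.** Both rest on assumed rates of 0.375 v 0.625. Step 5 shows 85% at a lower rate of 0.70.
- **That the type I error is inflated by two primaries.** This needs a rule that success on either question is enough, and the plan states no such rule. Even then the result depends on the test: about 3 to 6% family-wise with exact McNemar, about 8 to 10% with tests that attain roughly 5%.
- **That Figure 2 assigns questions inconsistently at the second viewing.** The extracted figure text is scrambled, so this cannot be judged and is not counted as an error.

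**Conclusion.** The concern holds as a gap in the definition of the primary endpoint and its test. The 72 subjects support the stated 25-point difference for one comparison pooled over both questions. They do not support it for each question separately over most of the table's correlation range. The shortfall is clear at correlations 0 to 0.4 and negligible (one subject, 79% power) at 0.5. These power figures depend on the unstated alpha, power and base rates inferred from the table, and on Figure 2 being balanced as section 4.1 describes. If rates are extreme, 36 pairs can reach 80% at low correlation.

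The test needs naming on any reading. Run unpaired, the chi-square is conservative rather than liberal, so it does not create false positives, but its true level is not the 5% a reader would assume. This should be fixed before analysis; pooled power is adequate, so the sample size need not change.

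**What to change.** In sections 3.1, 11.1, 17.2 and 17.3:

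1. Define one primary endpoint: correct answer (yes/no) after each website, pooled over the age and BMI questions.
2. Name one method that respects pairing, tested at two-sided 0.05. One option is logistic regression by GEE clustered on subject, with website, question and viewing order as factors and small-sample-corrected standard errors, and McNemar as a check. In simulation with 72 subjects this had size 0.041 to 0.048 and power of about 84 / 95 / 99% for 25 points at correlation 0 / 0.3 / 0.5, whether the question repeats or switches.
3. State the alpha, power and proportions behind the table, and whether a subject's question repeats or switches on the second website.
4. Make question-specific contrasts and the key-concepts measure secondary.

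If two primaries are kept instead, state whether either or both must succeed. If either suffices, use 0.025 each or Holm. If both must succeed, 0.05 each is valid, but joint power is lower than for either test alone. Restate the per-question detectable difference at 80% power. Under the assumed rates and alpha 0.05 it is about 0.36 / 0.30 / 0.25 at correlation 0 / 0.3 / 0.5 for 36 pairs (exact McNemar), or about 0.33 for 36 v 36 different subjects.

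The cost is wording only, with no extra subjects and no change to the visit. The downside is that claims about the age question alone or the BMI question alone become secondary, and the primary result is an average over the two.

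### Section 17.3 gives the ordered usefulness rating and the decisional-conflict score only a chi-square test and logistic regressions, with no stated method that uses category order and within-person pairing

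*Combined protocol and SAP*

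**What the plan says.** Section 3.2 names two kinds of secondary outcome. Perceived usefulness is an ordered rating: "Response choices to the questions will be based on a 5-point Likert-type scale". Satisfaction with decision-making and decisional conflict are measured "using the effective decision subscale of the Ottawa Decisional Conflict Scale", with no scoring rule, cut-point or time of collection.

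Section 4.1 describes a two-period crossover. One group sees the existing website and then the new one; "The other group will be shown the two websites in opposite order". On timing it says: "After viewing each website, responses to the intervention will be collected". Figure 2 shows only the primary outcome at each step.

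The method for every outcome is one sentence in section 17.3: "We will use a chi-square test and logistic regressions for analyzing primary and secondary measures". No section names an ordinal model, a rank test, a method for a score, a paired or clustered analysis, or a period term. Section 17.2, repeated in 11.1, introduces the sizing thus: "The table shows the required sample size for ranges of detectable differences and within-person correlation". Section 17.1 speaks of two arms: "We will examine group comparability at baseline between the two RCT arms".

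**The concern.** A chi-square test and logistic regression suit an answer that is right or wrong. A 1-to-5 rating enters a binary logistic model only after it is cut, and a score enters a chi-square test only after it is grouped. The plan supplies neither a cut nor a grouping. The ordinary forms of both methods also treat a person's two responses as if they came from different people, although the trial was sized on within-person correlation.

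What is at stake is the secondary conclusion on perceived value and decisional conflict. With positive within-person correlation an unpaired test has standard errors that are too large, so the main risk is that a real difference between the websites goes undetected. A lesser risk is that a cut-point is settled after the data are seen.

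**Working it through.** **The plan's own figure.** The documents give no effect size, spread, correlation or power for the secondary outcomes. The only sizing is the table in 17.2, for the primary proportion: 70 at a difference of 0.25 and correlation 0 (72 planned). Alpha, power and baseline are not stated, so it cannot be reproduced from the documents. It can be approximated with the paired-proportions formula

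n = [z_a·√ψ + z_b·√(ψ − d²)]² / d², where ψ is the discordant proportion.

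Assuming two-sided alpha 0.05, power 0.85 and proportions 0.29 and 0.54:
- ψ = 0.29×0.46 + 0.54×0.71 = 0.5168
- n = [1.96×0.719 + 1.036×0.674]² / 0.0625 = 71.1, so 72 against the stated 70

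The same inputs come close to all 45 filled cells. Alpha 0.10, power 0.90 and proportions centred on 0.50 fit 39 of 45. The inputs are therefore inferred, but the table looks paired.

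**Assumed inputs for the rating.** From the documents: 72 people, 36 per viewing order. Assumed: two-sided 0.05; latent normal scores cut so that the old website is rated 1 to 5 by 10/20/30/25/15%; a shift of 0.4 SD or 0.64 SD for the new website; correlation 0, 0.3 or 0.5; no period effect. At 0.64 SD, ratings of 4-5 rise from 40% to 65%. This matches the plan's 25 points, which were set for a proportion and not for this rating.

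**Simulated power at 0.4 SD.**

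| Analysis | corr. 0 | 0.3 | 0.5 |
|---|---|---|---|
| Unpaired 2x5 chi-square | 0.39 | 0.37 | 0.37 |
| Unpaired chi-square, ratings 4-5 v 1-3 | 0.49 | 0.50 | 0.50 |
| McNemar, ratings 4-5 v 1-3 | 0.46 | 0.57 | 0.66 |
| Unpaired rank test | 0.60 | 0.63 | 0.66 |
| Within-person, period-adjusted | 0.60 | 0.76 | 0.87 |

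The within-person row is a test on rating differences by viewing order. A separate run of 4,000 trials fitted the cumulative-logit model with person-clustered standard errors and gave 0.60/0.74/0.84. It gave 0.49/0.56/0.63 for McNemar and 0.41/0.38/0.34 for the 2x5 chi-square. The figures should be read to within about 4 points. With a 0.5 SD period effect added, that run gave 0.35/0.34/0.30 for the 2x5 chi-square and 0.58/0.72/0.82 for the model.

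**Closed-form check.** For an uncut normal score, SE = √[2(1 − ρ)/72] = 0.167/0.139/0.118. Then 0.4/SE = 2.40/2.87/3.39, and power = Φ(0.4/SE − 1.96) = 0.67/0.82/0.92. Five categories lose a little of this, in line with the last row.

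**Where the loss comes from.** At correlation 0 the gap between the 2x5 chi-square and the within-person analysis is 0.60 − 0.39 = 21 points, all from ignoring order. At 0.5 it is 0.87 − 0.37 = 50 points. Keeping order but not pairing still leaves 0.87 − 0.66 = 21.

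**At 0.64 SD.** The 4,000-trial run gave 0.83/0.85/0.89 for the 2x5 chi-square, 0.87/0.89/0.92 for chi-square on ratings 4-5 and 0.94/0.98/1.00 for the model. The gaps are 11/13/11 and 7/9/8 points. McNemar falls about 9/6/3 points short of the within-person analysis, and an unpaired rank test about 2 at most.

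**Under no difference.** At correlation 0.3 to 0.5 the unpaired chi-square tests reject in about 2-4% of trials, so they are conservative.

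**Carryover.** Suppose the websites do not differ, correlation is 0.5, and the old site is rated 0.2 or 0.4 SD lower when seen second. The within-person estimate is biased by half of that: 0.1/0.118 = 0.85 or 0.2/0.118 = 1.70 standard errors. On an uncut score the false-positive rate is then about 14% or 40%. Simulated on the rating, it is about 11% or 33%.

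**The case against.** The strongest reply is that 17.3 is terse, not wrong, and that the least favourable reading should not be pinned on it. Several kinder readings fit its words:

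- **Paired chi-square (McNemar type).** The within-person sizing table gives this some support. It restores pairing but, on a cut rating, loses order.
- **Trend chi-square or ordinal logistic regression.** Either restores order. A trend test gave 0.63/0.65/0.66 at 0.4 SD, much like the unpaired rank test. Pairing is still lost.
- **First viewings only.** The mention of two arms in 17.1 could mean this. Chi-square is then valid and free of carryover, but half of the responses go unused. At 0.4 SD, chi-square power is 19-27%. Even an uncut score reaches only 0.4/√(2/36) = 1.70, or power of about 0.40.

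Much of this stands. The gap is one of specification, and its size depends on the reading and on an assumed 0.4 SD shift with no basis in the documents. At 0.64 SD most of the gap closes. Collection of the subscale after each website is implied by 4.1 but not stated. The within-person model also has a weakness that a first-viewing comparison avoids: it assumes no differential carryover.

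What does not stand is that these points remove the need for a change. None of the readings is written down, and each of those listed gives up some order, pairing or data.

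**Conclusion.** The point holds as a gap in the stated method for secondary outcomes. If the ordinary unpaired or dichotomised analysis is meant, the assumed cost is about 21 to 50 points of power at 0.4 SD for the 2x5 test, and about 11 to 13 at 0.64 SD. If an unpaired ordinal method is meant, the cost runs from nothing at correlation 0 to about 21 points at 0.5 for a 0.4 SD shift, and is about 2 points at most at 0.64 SD. All of these rest on assumed distributions, shifts and correlations.

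A reader might infer three stronger things that the documents do not support:

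- That the named tests are invalid or inflate false positives. They are conservative under positive correlation. Keeping the better of two cut-points after seeing the data would give roughly 4-10%, but nothing in the plan says this will be done.
- That the plan commits to the least favourable test. It does not say which form is meant.
- That the subscale is certainly collected twice per person. Its timing is not stated.

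Only secondary conclusions are affected. Priority is low to moderate.

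**What to change.** In section 17.3, give the 3.2 outcomes their own methods.

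- **Usefulness rating.** Cumulative-logit model with website and period terms and person-clustered standard errors, reporting the website odds ratio with 95% CI. Add site, the stratification factor in 4.1, if more than one site contributes; section 18.4 has 50 of the 72 coming from HHS.
- **Carryover check.** As a sensitivity analysis, compare first viewings between the two orders, also by an ordinal method. Its power is low, so use it to judge direction and size. A signed-rank test is optional.
- **Decisional-conflict subscale.** State its scoring and when it is collected. If it is collected after each website, analyse the undichotomised score with a within-person model with the same terms, and report the website difference with 95% CI. If it is collected once, compare the two viewing orders and say which question that answers.
- **Dichotomised results.** Descriptive only, with the cut-point fixed in advance.

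The cost is wording: the same data, standard software and no added participants. The downsides are the proportional-odds assumption, the assumption of no differential carryover (false-positive rates of about 11% or 33% in the cases worked above) and slightly more analysis work. If such a model was already intended, a few sentences close the point.
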